#### **10.1.2.** Reporting Procedure

All events (serious and non-serious) must be reported with the investigator's assessment of the event's seriousness, severity, and causality to the (when applicable: blinded) study drug. For SAEs and AESIs, a detailed narrative summarizing the course of the event, including its evaluation, treatment, and outcome should be provided on the AE CRF. Specific or estimated dates of event onset, treatment, and resolution should be included, when available. Medical history, concomitant medications, and laboratory data that are relevant to the event should also be summarized in the narrative. For fatal events, the narrative should state whether an autopsy was or will be performed, and include the results if available. Information not available at the time of the initial report must be documented in a follow-up report. Source documents (including hospital or medical records, diagnostic reports, etc.) will be summarized in the narrative on the AE CRF, and retained at the study center and available upon request.

Urgent safety queries must be followed up and addressed promptly. Follow-up information and response to non-urgent safety queries should be combined for reporting to provide the most complete data possible within each follow-up.

## 10.1.3. Events that Require Expedited Reporting to Sponsor

The following events also require reporting to the sponsor (or designee) within 24 hours of learning of the event:

- SAEs.
- Adverse Events of Special Interest (AESI; serious and nonserious): Adverse events of special interest for this study include the following:
  - Anaphylactic reactions
  - Systemic hypersensitivity reactions
  - Helminthic infections
  - Clinically symptomatic eosinophilia (or eosinophilia associated with clinical symptoms)
  - Any severe type of conjunctivitis or blepharitis
  - Keratitis
  - Severe injection site reactions
  - Herpes simplex infection
  - Arthralgia
- **Pregnancy:** Although pregnancy is not considered an AE, it is the responsibility of the investigator to report to the sponsor (or designee), within 24 hours of identification, any pregnancy occurring in a female study patient during the study or within 12 weeks of the last dose of study drug. Any complication of pregnancy affecting a female study patient, and/or fetus and/or newborn that meets the SAE criteria must be reported as an SAE. Outcome for all pregnancies should be reported to the sponsor.

Regeneron Pharmaceuticals, Inc.

#### CONFIDENTIAL

## **10.2.** Definitions

## 10.2.1. Adverse Event

An AE is any untoward medical occurrence in a patient administered a study drug which may or may not have a causal relationship with the study drug. Therefore, an AE is any unfavorable and unintended sign (including abnormal laboratory finding), symptom, or disease which is temporally associated with the use of a study drug, whether or not considered related to the study drug (ICH E2A Guideline. Clinical Safety Data Management: Definitions and Standards for Expedited Reporting, Oct 1994).

## 10.2.2. Serious Adverse Event

An SAE is any untoward medical occurrence that at any dose:

- Results in **death** includes all deaths, even those that appear to be completely unrelated to study drug (eg, a car accident in which a patient is a passenger).
- Is **life-threatening** in the view of the investigator, the patient is at immediate risk of death at the time of the event. This does not include an AE that had it occurred in a more severe form, might have caused death.
- Requires in-patient **hospitalization** or **prolongation of existing hospitalization**. Inpatient hospitalization is defined as admission to a hospital (any duration) or an emergency room visit for longer than 24 hours. Prolongation of existing hospitalization is defined as a hospital stay that is longer than was originally anticipated for the event, or is prolonged due to the development of a new AE as determined by the investigator or treating physician.
- Results in persistent or significant **disability/incapacity** (substantial disruption of one's ability to conduct normal life functions).
- Is a **congenital anomaly/birth defect**
- Is an **important medical event**. Important medical events may not be immediately lifethreatening or result in death or hospitalization, but may jeopardize the patient or may require intervention to prevent one of the other serious outcomes listed above (eg, intensive treatment in an emergency room or at home for allergic bronchospasm; blood dyscrasias or convulsions that do not result in hospitalization; or development of drug dependency or drug abuse).

Criteria for reporting SAEs must be followed for these events.

#### **10.2.3.** Adverse Events of Special Interest

An AESI, serious or non-serious, is one of scientific and medical interest specific to the sponsor's product or program, for which ongoing monitoring and rapid communication by the investigator to the sponsor can be appropriate. Such an event might warrant further investigation in order to characterize and understand it.

Regeneron Pharmaceuticals, Inc.

## 10.2.4. Severity

The severity of AEs will be graded according to the following scale:

**Mild:** Does not interfere in a significant manner with the patient's normal functioning level. It may be an annoyance. Prescription drugs are not ordinarily needed for relief of symptoms, but may be given because of personality of the patient.

**Moderate:** Produces some impairment of functioning but is not hazardous to health. It is uncomfortable or an embarrassment. Treatment for symptoms may be needed.

**Severe:** Produces significant impairment of functioning or incapacitation and is a definite hazard to the patient's health. Treatment for symptom may be given and/or patient hospitalized.

If a laboratory value is considered an AE, its severity should be based on the degree of physiological impairment the value indicates.

#### **Injection Site Reactions**

The severity of injection site reactions will be graded according to the following scale (semi-colon indicates "or" within description of grade:

**Mild**: Pain that does not interfere with activity; mild discomfort to touch; <5 cm of erythema or induration that does not interfere with activity

**Moderate**: Pain that requires repeated use of non-narcotic pain reliever >24 hours or interferes with activity; discomfort with movement; 5.1 cm to 10 cm erythema or induration or induration that interferes with activity

**Severe**: Pain that requires any use of narcotic pain reliever or that prevents daily activity; significant discomfort at rest; >10 cm erythema or induration; prevents daily activity; requires emergency room visit or hospitalization; necrosis or exfoliative dermatitis

## 10.2.5. Causality

The investigator must provide causality assessment as to whether or not there is a reasonable possibility that the drug caused the AE, based on evidence or facts, his/her clinical judgment, and the following definitions. The causality assessment must be made based on the available information and can be updated as new information becomes available.

For double-blinded studies using an active comparator, the investigator should consider all study drugs in determining event causality.

The following factors should be considered when assessing causality:

- Temporal relationship: time to onset versus time drug was administered
- Nature of the reactions: immediate versus long term
- Clinical and pathological features of the events
- Existing information about the drug and same class of drugs
- Concomitant medications
- Underlying and concurrent illnesses
- Response to dechallenge (drug discontinuation) or dose reduction
- Response to rechallenge (re-introduction of the drug) or dose increase, when applicable
- Patient's medical and social history

Causality to the study drug (including study drug administration):

- Related:
  - The AE follows a reasonable temporal sequence from study drug administration, and cannot be reasonably explained by the nature of the reaction, patient's clinical state (eg, disease under study, concurrent diseases, concomitant medications), or other external factors.
  - or
  - The AE follows a reasonable temporal sequence from study drug administration, and is a known reaction to the drug under study or its class of drugs, or is predicted by known pharmacology.
- Not Related:
  - The AE does not follow a reasonable sequence from study drug administration, or can be reasonably explained by the nature of the reaction, patient's clinical state (eg, disease under study, concurrent diseases, and concomitant medications) or other external factors.

Causality to the study conduct (protocol-specified procedure):

- Related:
  - The AE follows a reasonable temporal sequence from a protocol-specified procedure, and cannot be reasonably explained by the nature of the reaction, patient's clinical state (eg, disease under study, concurrent diseases, concomitant medications), or other external factors.
- Not Related:
  - The AE does not follow a reasonable sequence from a protocol-specified procedure, or can be reasonably explained by the nature of the reaction, patient's clinical state

(eg, disease under study, concurrent diseases, and concomitant medications) or other external factors.

# 10.3. Safety Monitoring

The investigator will monitor the safety of study patient at his/her site(s) as per the requirements of this protocol and consistent with current Good Clinical Practice (GCP). Any questions or concerns should be discussed with the sponsor in a timely fashion. The sponsor will monitor the safety data from across all study sites. The medical/study director will have primary responsibility for the emerging safety profile of the compound, but will be supported by other departments (eg, Pharmacovigilance; Risk Management; Biostatistics and Data Management). Safety monitoring will be performed on an ongoing basis (eg, individual review of SAEs) and on a periodic, cumulative aggregate basis.

# 10.4. Notifying Health Authorities, Institutional Review Board/Ethics Committee, and Investigators

During the study, the sponsor and/or the CRO will inform health authorities, ECs/institutional review boards (IRBs), and the participating investigators of any SUSARs (suspected unexpected serious adverse reactions) occurring in other study centers or other studies of the active study drug dupilumab, as appropriate per local reporting requirements. In addition, the sponsor and/or CRO will comply with any additional local safety reporting requirements. All notifications to investigators will contain only blinded information.

Upon receipt of the sponsor's notification of a SUSAR that occurred with the study drug, the investigator will inform the IRB/EC unless delegated to the sponsor.

Event expectedness for study drug (dupilumab) is assessed against the Reference Safety Information section of the Investigator's Brochure that is effective for expedited safety reporting.

At the completion of the study, the sponsor will report all safety observations made during the conduct of the trial in the CSR to health authorities and ECs/IRB as appropriate.

# 11. STATISTICAL PLAN

This section provides the basis for the SAP for the study.

Endpoints are listed in Section 4. Analysis variables are listed in Section 5.

Data collected through the implementation of new CRFs regarding the impact of the COVID-19 pandemic on patients will be summarized (eg, discontinuation due to COVID-19). Any additional analyses and methods required to investigate the impact of COVID-19 on the efficacy (eg, missing data due to COVID-19) and safety evaluation will be specified in the SAP.

## **11.1.** Statistical Hypothesis

The following null hypothesis and alternative of the primary endpoint will be tested for the comparison of each dupilumab treatment group to placebo for Part A:

- Null hypothesis (H0): The success rate (where success is achieving peak esophageal intraepithelial eosinophil count of ≤6 eos/hpf at week 16) is equal between dupilumab groups (higher exposure group or lower exposure group) and placebo.
- Alternative hypothesis (H1): The success rate differs at week 16 between dupilumab and placebo.

No formal hypothesis and adjustment for multiplicity will be undertaken for Parts B and C.

# **11.2.** Justification of Sample Size

The planned sample size is a total of approximately 90 patients (1:1:1 ratio, 30 patients in the higher dupilumab exposure group, 30 patients in the lower dupilumab exposure group, and 30 patients in the placebo group). See Section 3.2.2 for dose selection rationale.

The assumptions used in sample size calculation were based on Part A of the R668-EE-1774 study (a phase 3 study for adults and adolescents with EoE) and R668-EE-1324 (a phase 2 study for adults with EoE). In Part A of the R668-EE-1774, the proportions of patients achieving a peak esophageal intraepithelial eosinophil count of ≤6 eos/hpf at week 24 were 59.5% and 5.1% for dupilumab and placebo, respectively. In Part A of the R668-EE-1774, the proportions of adolescent patients achieving peak esophageal intraepithelial eosinophil count of  $\leq 6 \text{ eos/hpf}$  at week 24 were 36.4% and 0% for dupilumab and placebo, respectively. The treatment group difference observed in adolescents was approximately 36.5%. In the R668-EE-1324 study, the proportions of patients achieving histologic response at week 12 were 65% and 0% for dupilumab and placebo, respectively. The efficacy of dupilumab can be established as early as week 12. Based upon the similarity of pathophysiology and expected similarity of response between adults and pediatric patients, a similar proportion of responders at week 16 was assumed for sample size calculation. The lower exposure dupilumab group is assumed to have a similar treatment effect to the higher exposure dupilumab group. The treatment group difference observed in the R668-EE-1774 Part A adolescents was assumed for the sample size calculation for this study in children aged  $\geq 1$  year to < 12 years. It is estimated that with a total number of 90 patients (30 patients in the higher exposure dupilumab group, 30 patients in the lower exposure dupilumab group, and 30 patients in the placebo group), at the 2-sided 5% significance level using Fisher's exact test, the study can provide 95% power to detect a treatment difference of 35.6% in the proportion of

Regeneron Pharmaceuticals, Inc.

histologic responders (ie, patients achieving peak esophageal intraepithelial eosinophil count  $\leq 6 \operatorname{eos/hpf}$ ) at week 16 between placebo (5.1%) and each dupilumab treatment group (40.7%).

Sample size calculations were made using nQuery Advisor 7.0.

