#### Sample Size:

The planned sample size is a total of approximately 90 patients (1:1:1 ratio, 30 patients in the higher dupliumab exposure group and 30 patients in the lower dupliumab exposure group and 30 patients in the placebo group).

The assumptions used in sample size calculation were based on Part A of the R668-EE-1774 study (a phase 3 study for adults and adolescents with EoE) and R668-EE-1324 (a phase 2 study for adults with EoE). In Part A of the R668-EE-1774, the proportions of patients achieving peak esophageal intraepithelial eosinophil count of ≤6 eos/hpf at week 24 were 59.5% and 5.1% for dupilumab and placebo, respectively. The proportions of adolescent patients achieving peak esophageal intraepithelial eosinophil count of  $\leq 6$  eos/hpf at week 24 were 36.4% and 0% for dupilumab and placebo, respectively. The treatment group difference observed in adolescents was approximately 36.5%. In the R668-EE-1324 study, the proportions of patients achieving histologic response at week 12 were 65% and 0% for dupilumab and placebo, respectively. The efficacy of dupilumab can be established as early as week 12. Based upon the similarity of pathophysiology and expected similarity of response between adults and pediatric patients, a similar proportion of responders at week 16 was assumed for sample size calculation. The lower exposure dupilumab group is assumed to have a similar treatment effect as the higher exposure dupilumab group. The treatment group difference observed in the R668-EE-1774 Part A adolescents was assumed for the sample size calculation for this study in children aged  $\geq 1$  year to <12 years. It is estimated that with a total number of 90 patients (30 patients in the higher exposure dupilumab group, 30 patients in the lower exposure dupilumab group, and 30 patients in the placebo group), at the 2-sided 5% significance level using Fisher's exact test, the study can provide 95% power to detect a treatment difference of 35.6% in the proportion of histologic responders (ie, patients achieving peak esophageal intraepithelial eosinophil count  $\leq 6 \text{ eos/hpf}$ ) at week 16 between placebo (5.1%) and each dupilumab treatment group (40.7%).

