#### 11.4.3. Efficacy Analyses

#### 11.4.3.1. Primary Efficacy Analysis

The primary analysis of proportion of patients achieving a histologic response of peak esophageal intraepithelial eosinophil count  $\leq 6 \text{ eos/hpf}$  at week 16 will be analyzed using the Cochran-Mantel-Haenszel (CMH) test to assess the difference in the proportion of responders in the FAS, adjusting for the randomization stratification factor (baseline weight group). The randomization stratification of baseline weight group may be pooled to ensure the sufficient sample size of each stratum.

For the primary estimands of interest for the primary endpoint, the intercurrent events, strategies, and the corresponding missing data handling approaches are provided as below:

	Estimands				
Endpoint Category	Endpoint(s)	Population	Intercurrent event(s) strategy and missing data handling	Population-level summary/Analysis	
Primary Endpoint	Proportion of patients achieving peak esophageal intraepithelial eosinophil count of ≤6 eos/hpf (400×) at week 16	FAS	
 
The intercurrent events will be handled as follows:
 
Treatment discontinuation: data collected after the patient discontinued treatment will be included in the analysis (Treatment policy strategy)
 
Initiation of treatment with systemic and/or swallowed topical corticosteroids drugs: patients will be considered as non-responders after such event (composite variable strategy)
 
Note: the composite strategy will be considered if a patient receives rescue medication any time during the study.
 
Missing data handling: patients with a missing value for the primary endpoint at week 16 due to study discontinuation or other reasons will be considered to be non-responders
 
	Cochran-Mantel-Haenszel (CMH) test adjusting for the randomization stratification factor (baseline weight group) will be utilized. The estimated proportion of the treatment difference between dupilumab groups and placebo, and its 2-sided 95% confidence intervals will be provided based on the CMH test.	

Sensitivity analyses will assess alternative methods to impute missing data. The sensitivity analyses will include tipping point analysis approach and worst observation carried forward – multiple imputation (WOCF-MI) approach.

Subgroup analyses (eg, by weight) may be performed. Details will be specified in the SAP.

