#### **11.4.4.** Control of Multiplicity

For multiplicity adjustment, a hierarchical procedure will be used to control the overall Type-1 error rate at 0.05 for the primary endpoint and the selected secondary efficacy endpoints for each dupilumab dose regimen versus placebo in Part A only. Each hypothesis will be formally tested only if the preceding one is significant at the 2-sided 0.05 significance level. The primary endpoint will be tested for the higher exposure dupilumab group first and then for the lower exposure dupilumab group. The hierarchical order of the secondary endpoints will be specified in the SAP.

As Part B and C data will be summarized using descriptive statistics, there is no multiplicity issue.

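### The stated 95% power does not belong to Fisher's exact test: 30 per arm at 5.1% vs 40.7% gives 90.1%, while the planned CMH test gives about 95%

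*Protocol*

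**What the plan says.** Section 11.2 plans about 90 patients randomized 1:1:1, so each dupilumab group is compared with placebo on 30 against 30. The calculation is made "at the 2-sided 5% significance level using" Fisher's test, and the sentence continues: "exact test, the study can provide 95% power to detect a treatment difference of 35.6% in the proportion of" histologic responders at week 16, "between placebo (5.1%) and each dupilumab treatment group (40.7"%). The synopsis makes the same statement: "the study can provide 95% power to detect a treatment difference of 35.6% in the proportion of histologic responders".

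On the origin of the effect size, Section 11.2 gives adolescent response rates of 36.4% and 0% from Part A of the adult and adolescent phase 3 study. It then says "The treatment group difference observed in adolescents was approximately 36.5"%, and later "The treatment group difference observed in the R668-EE-1774 Part A adolescents was assumed for the sample size calculation".

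The primary analysis in Section 11.4.3.1 uses a different test: the responder proportion "will be analyzed using the Cochran-Mantel-Haenszel (CMH) test to assess the difference in the proportion of responders in the FAS", adjusted for baseline weight group. Section 11.4.4 orders the two primary comparisons, higher exposure first, without splitting alpha: "Each hypothesis will be formally tested only if the preceding one is significant at the 2-sided 0.05 significance level".

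**The concern.** Every input needed to reproduce the power is printed: the test, the level, the two rates and the group size. Fisher's exact test is conservative in small samples with a low control rate, so 95% at 30 per arm looked too high for it. The test named for planning is also not the test planned for analysis.

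At stake is whether the justification for 30 per arm can be checked. As written, a reader cannot tell whether the risk of missing the assumed effect in one comparison is about 10% (the named test) or about 5% (the planned test). Nor can the reader tell which effect was assumed, because the paragraph gives three values for what it presents as one difference.

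**Working it through.** **Inputs** (Section 11.2 unless noted): n = 30 per group; placebo rate p0 = 0.051; dupilumab rate p1 = 0.407; two-sided alpha = 0.05. Each exposure group is compared separately with placebo (Section 11.1), and each test in the sequence is at the full 0.05 (Section 11.4.4).

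**Formula.** Let X be the placebo responders, Bin(30, 0.051), and Y the dupilumab responders, Bin(30, 0.407). Exact power is the sum of P(X = x) P(Y = y) over all of the 31 × 31 tables in which the test rejects.

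- Fisher rejects when the two-sided exact p ≤ 0.05.
- CMH with one stratum rejects when (x − m/2)² / V > 3.841, where m = x + y and V = 30·30·m(60 − m) / (60²·59).

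**Why the two tests differ.** Take no placebo responders.

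- Fisher with 5 dupilumab responders: p = 2·C(30,5)/C(60,5) = 2 × 142,506 / 5,461,512 = 0.052, not significant. With 6: p = 2 × 593,775 / 50,063,860 = 0.024, significant.
- CMH with 4 dupilumab responders: V = 900·4·56 / 212,400 = 0.949, and 2² / 0.949 = 4.21, already significant.

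**Attempt to reproduce the stated 95%, by number of placebo responders:**

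| x | P(X = x) | Fisher: y needed | P(reject given x) | Product | CMH: y needed | P(reject given x) | Product |
|---|---|---|---|---|---|---|---|
| 0 | 0.2080 | 6 | 0.9954 | 0.2070 | 4 | 0.9998 | 0.2079 |
| 1 | 0.3353 | 8 | 0.9631 | 0.3229 | 6 | 0.9954 | 0.3338 |
| 2 | 0.2613 | 9 | 0.9183 | 0.2399 | 8 | 0.9631 | 0.2516 |
| 3 | 0.1310 | 11 | 0.7348 | 0.0963 | 10 | 0.8431 | 0.1105 |
| 4 | 0.0475 | 12 | 0.5996 | 0.0285 | 11 | 0.7348 | 0.0349 |
| 5 | 0.0133 | 13 | 0.4526 | 0.0060 | 12 | 0.5996 | 0.0080 |
| 6 | 0.0030 | 15 | 0.1966 | 0.0006 | 14 | 0.3130 | 0.0009 |

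Unrounded totals over all tables: **Fisher 0.9013, CMH 0.9477**. The uncorrected Pearson chi-square also gives 0.9477. The stated 95% is not reproduced for Fisher's test; the gap is 4.9 points.

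**Other readings of the Fisher calculation:**

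- Doubled one-sided p, or one-sided alpha of 0.025: 90.1%.
- 5.1% plus 36.4 points (41.5%): 91.3%. Plus 36.5 points (41.6%): 91.4%.
- Literal adolescent rates, 36.4% vs 0%: 98.4%.
- Both dupilumab groups pooled, 60 vs 30: 98.2%, but this is not the stated comparison.
- One-sided alpha of 0.05: 94.5%, but the text says two-sided.

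**Fisher by group size at 40.7% vs 5.1%:** 34 per arm 94.2%; 35 per arm 94.97%; 36 per arm 95.6%.

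**CMH with weight strata.** The stratum sizes are assumptions, since the protocol does not give them. With a common response rate in all strata and 400,000 simulated trials per layout, power for two or three strata (per-arm sizes such as 10/10/10, 5/15/10, 3/15/12 and 15/15) ran from 94.8% to 95.0%. With a continuity correction, single-stratum CMH falls to 89.9%.

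**The difference.** Adolescent rates: 36.4 − 0 = 36.4 points. Printed adolescent difference: about 36.5. Used in the calculation: 40.7 − 5.1 = 35.6. The last is internally consistent, but it is not the difference said to have been assumed.

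**The case against.** The strongest case on the other side is that little follows from this. The planned analysis is CMH, for which 95% is about right, so the trial is no smaller than intended. The current protocol also reports in its Introduction that Part A met its primary endpoint for both exposures (p < 0.0001), so restating prospective power cannot change enrolment or inference. That is correct, and it is why the request is limited to wording. It does not make the printed figure right: the sentence still stands as the sample size justification, and it names a test that does not give that power.

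A second objection is that CMH need not be the source of the 95%. This stands. An unpooled normal approximation gives 95.2% and an arcsine approximation 94.9%, and the protocol does not show which method produced its figure. The point here is only that two-sided Fisher did not.

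Third, 94.8% for CMH is conditional on no continuity correction and a common effect across weight groups. This also stands, and the corrected text should state both conditions.

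Fourth, 36.5% is labelled approximate and lies only 0.1 point from 36.4%. That gap alone is trivial. The gap between either value and 35.6% is not explained by rounding, though it moves Fisher power only from 90.1% to 91.3–91.4%.

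**Conclusion.** The concern holds. With the protocol's own inputs, the two-sided 5% Fisher's exact test has 90.1% power per comparison, not 95%, so the type II error is about twice what the statement implies. No difference printed in Section 11.2, added to the stated 5.1% placebo rate, brings Fisher's test to 95% at 30 per arm. The planned CMH test has 94.8%, assuming no continuity correction and a common effect across weight strata, so the sample size is not in question. Separately, the difference used (35.6%) does not match the one said to have been assumed (36.4% from the rates, about 36.5% as printed).

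The Fisher result is exact and needs no assumption beyond the stated inputs. Only the stratified CMH range depends on assumed stratum sizes.

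**What to change.** In Section 11.2 and the synopsis, replace the power sentence with one to this effect: with 30 patients per group and response rates of 5.1% and 40.7%, power for each comparison at the two-sided 5% level is about 90% by Fisher's exact test and about 95% by the CMH test used for the primary analysis (without continuity correction, assuming a common effect across weight groups).

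In the same two places, reconcile the effect size. Print the adolescent difference as 36.4%, which is what the quoted rates give, or explain why 36.5% differs. Then state whether that difference or 35.6% was the planning assumption and, if 35.6%, where it comes from.

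Optionally, because the lower exposure is tested only after the higher one succeeds, add that the probability of both being significant is about 91% under CMH if both arms have a 40.7% response. The protocol makes no claim about this, so it is context and not a correction.

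The cost is wording in two places, with no change to the sample size, design or analysis.

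### The 95% power stated for each dupilumab group takes no account of the fixed testing sequence, under which the lower-exposure test has about 91%

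*Protocol*

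**What the plan says.** Protocol section 11.2, repeated in the synopsis, sets 30 patients per arm and states that "the study can provide 95% power to detect a treatment difference of 35.6" percentage points, with the rates given as "between placebo (5.1%) and each dupilumab treatment group (40.7"%). The calculation is said to be "at the 2-sided 5% significance level using Fisher's exact test". On the two doses, the section adds: "The lower exposure dupilumab group is assumed to have a similar treatment effect to the higher exposure dupilumab group".

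Section 11.4.4 fixes the order of testing: "The primary endpoint will be tested for the higher exposure dupilumab group first and then for the lower exposure dupilumab group". The gate is explicit: "Each hypothesis will be formally tested only if the preceding one is significant at the 2-sided 0.05 significance level".

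Section 11.2 does not mention this order. Section 11.4.3.1 analyses the primary endpoint with a CMH test adjusted for baseline weight group, not with Fisher's exact test.

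**The concern.** A power figure attached to each of two comparisons reads as the chance of success for each. In this design that holds for the higher-exposure group, which is tested first at the full two-sided 0.05. It does not hold for the lower-exposure group. Its null hypothesis can be rejected only when the higher-exposure test and its own test are both significant, and both use the same placebo patients. Its power is therefore a joint probability and must be below the single-comparison figure.

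What is at stake is the accuracy of the sample size justification for the lower-exposure claim. A reader of 11.2 would put the chance of missing a true effect there at about 1 in 20, when the plan's assumptions imply about 1 in 11. Type I error control is not in question.

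**Working it through.** **Inputs.** From 11.2: n = 30 per arm; response 0.051 on placebo and 0.407 in each dupilumab group; two-sided 5%; Fisher's exact test; similar effect in both groups, taken here as equal. From 11.4.4: higher exposure first, lower exposure only if the first is significant. From 11.4.3.1: CMH as the planned test, with missing outcomes counted as non-response, so the assumed rates are taken to include dropout.

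**Formulas.** Let X ~ Bin(30, 0.051) be the placebo responders, and q(x) the probability that a dupilumab arm, Bin(30, 0.407), has enough responders to be significant against x placebo responders.

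- Power per comparison = Σ P(X = x) · q(x)
- Power of the lower-exposure test behind the gate = Σ P(X = x) · q(x)²

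The square arises because, given the placebo count, the two dupilumab arms are independent and have the same assumed rate.

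**Step 1: the plan's own figure.** Two-sided Fisher gives 90.1% per comparison, not 95%. Figures near 95% come from other calculations: uncorrected chi-square or unstratified CMH 94.8%, unpooled z 95.2%, arcsine 94.9%, one-sided 5% Fisher 94.5%. The stated 95% is thus not the power of the named test, but it is close to that of an uncorrected CMH test.

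**Step 2: the gate, using a test that does give about 95%.** Unstratified CMH without continuity correction:

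| Placebo responders x | P(X = x) | Dupilumab responders needed | q(x) | P·q | P·q² |
|---|---|---|---|---|---|
| 0 | 0.2080 | 4 | 0.9998 | 0.2079 | 0.2079 |
| 1 | 0.3353 | 6 | 0.9954 | 0.3338 | 0.3322 |
| 2 | 0.2613 | 8 | 0.9631 | 0.2516 | 0.2423 |
| 3 | 0.1310 | 10 | 0.8431 | 0.1105 | 0.0932 |
| 4 | 0.0475 | 11 | 0.7348 | 0.0349 | 0.0257 |
| 5 | 0.0133 | 12 | 0.5996 | 0.0080 | 0.0048 |
| 6 or more | small | 14 or more | 0.313 or less | 0.0010 | 0.0003 |
| Sum | | | | **0.948** | **0.906** |

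The gate costs 94.8 − 90.6 = 4.2 points. The lower group's type II error goes from 5.2% to 9.4%. If the two tests were independent the joint power would be 0.948² ≈ 0.898; the shared placebo arm recovers a little of the loss.

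**Step 3: checks on that figure.**

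- CMH stratified by weight, simulated with 300,000 runs for each of three assumed splits per arm (5/15/10, 3/15/12, 10/10/10), gives 90.7% to 90.9% behind the gate. The protocol gives no stratum sizes, so the splits are assumptions.
- Accepting single-test power as exactly 95%, the correlation from the shared placebo arm is 0.051·0.949 / (0.051·0.949 + 0.407·0.593) = 0.0484/0.2898 = 0.17. The bivariate normal joint power is then 90.5% (90.3% at correlation 0, 91.2% at 0.5).

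**Step 4: sensitivity to the equal-effect assumption.** CMH power for the lower group behind the gate, with placebo at 5.1%:

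| Higher exposure | Lower exposure | Gated power |
|---|---|---|
| 40.7% | 40.7% | 90.6% |
| 45% | 40.7% | 93.0% |
| 50% | 40.7% | 94.2% |
| 59.5% | 40.7% | 94.7% |
| 40.7% | 36.4% | 86.4% |

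The rates 59.5% and 36.4% are the overall and adolescent dupilumab rates that 11.2 quotes from the adult and adolescent phase 3 study; 45% and 50% are illustrative.

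**Step 5: the named test behind the gate.** Two-sided Fisher gives 82.8%. The distance from 95% has two parts: 95 − 90.1 = 4.9 points because the stated figure does not belong to that test, and 90.1 − 82.8 = 7.3 points from the gate.

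**The case against.** The strongest reply is that 11.2 gives power per comparison, as is common, and matches section 11.1, which sets a hypothesis for each dupilumab group against placebo. The protocol nowhere claims 95% for both tests together. On that reading the gate is an unreported operating characteristic, and with CMH the lower group still has about 91%. That stands as a description of what was probably calculated, and it limits the weight of the point. It does not rescue the figure: the protocol itself fixes the order and applies 95% to each group, so what it states for the lower group is not that group's power under the procedure it prescribes. Even as a per-comparison figure, 95% is not what the named Fisher test gives.

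Three stronger readings are tempting, and the document does not support them.

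- A reader might infer that the gate reduces power from 95% to 83%. That charges the Fisher discrepancy to the gate, and 83% is not the power of the planned CMH analysis.
- A reader might take 91% as a ceiling. It is the value at 40.7% in both groups; a better response in the higher group brings it close to the single-test figure.
- A reader might conclude that the trial is underpowered for its primary objective. Section 2.1 asks for efficacy of dupilumab treatment against placebo and does not require both regimens to succeed.

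It is also fair to say that little now turns on this: sections 1 and 3.3.1.1 report that Part A met its primary endpoint for both regimens, with p-values below 0.0001.

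**Conclusion.** The point holds as a misstatement in the sample size justification. With 30 per arm, 5.1% on placebo, 40.7% in both dupilumab groups and a shared placebo arm, the lower-exposure test has about 91% power under the fixed sequence when the single-comparison power is about 95%. The gate itself costs about 4 points and takes the lower group's type II error from about 5% to about 9%. The higher-exposure figure is not affected by the gate.

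The size rests on the equal-effect assumption and on an uncorrected CMH test; stratifying by weight changes it little under the splits tried. The 4.9-point gap between 95% and the named Fisher test's 90.1% is a separate error. The point concerns the design justification only and does not alter the reported Part A result.

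**What to change.** In 11.2 and the synopsis:

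- give the higher-exposure power as the single-test figure;
- give the lower-exposure power as the joint figure under the sequence in 11.4.4, about 91% with CMH;
- say that both figures assume 40.7% in each dupilumab group;
- name the test to which they belong. If Fisher's exact test is kept, the corresponding figures are 90.1% and 82.8%.

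The cost is a sentence or two in two places and a less favourable figure for the lower group. Sample size, testing order and analysis stay as they are.
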